#### Drug administration

- Study drug will be administered orally on a twice daily basis (bid). **At all clinic visits the study drug will be administered at the study site (after any sampling procedures and PFTs).** The patients should swallow the study medication unchewed together with a glass of water (~250 mL), and should observe a dose interval of approximately 12 hours. Study drug needs to be taken at approximately the same time every day (preferably between 06:00 and 11:00 in the morning, and between 18:00 and 23:00 in the evening).
- Because nintedanib may cause stomach discomfort, it is recommended to take the administered drug after the meal.
- If a dose of nintedanib is missed, i.e. not taken between 06:00 and 11:00 in the morning, and between 18:00 and 23:00 in the evening, administration should resume at the next scheduled time at the recommended dose. No catch up of missed doses is permitted.

Patients experiencing adverse effects requiring temporary drug discontinuation (refer to [Section 4.2.1](#) and [4.2.2](#)) may start to receive study drug at 100 mg bid. The dose can also be reduced without prior discontinuation, i.e. immediately stepping down from 150 mg bid to 100 mg bid if necessary. In the case of severe toxicity or when the reduced dose is again not tolerated, drug treatment must be stopped and cannot be restarted. All dose reductions must be approved by the Investigator or delegated site staff at the site (during the scheduled or unscheduled visit) and the reason for reduction must be documented.

In case of adverse events requiring dose reduction (refer to [Sections 4.2.1](#) and [4.2.2](#)), 100 mg bid (or matching placebo) will be assigned by IRT upon call of the Investigator. The colour of the 150 mg capsules and the 100 mg capsules will be slightly different; the packaging will remain the same (same number of capsules per blister, same number of blisters per box).

If the reduced dose is well tolerated, re-escalation to 150 mg bid is possible, according to procedures described in [Section 4.2.1.1](#).

The amount of study drug dispensed at the time of dose reduction and dose re-escalation is dependent upon the amount of time between the unscheduled visit and the next planned study visit. Therefore at unscheduled visits for dose reductions and dose re-escalations, IRT will assign only the number of boxes of study medication needed until the next predicted planned patient visit as noted within the IRT system.

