## **Visit 5**

Optional - Call the patient the day before the clinic visit to remind the clinic visit next day. Remind the patient medication washout requirements (if applicable) and to bring all study related supplies ( , patient diary, treatments, etc.) to the clinic visit.

- Review and discuss new Patient Diary entries with the patient
- Review and record all adverse events experienced and changes in concomitant therapy
- Record vital signs (blood pressure and pulse rate) before PFTs and with the patient seated and rested for at least five minutes
- Record patient weight
- Perform safety laboratory collections and urine pregnancy test (if applicable). For further details refer to [Section 5.3.3](#)
- Collect biomarker serum and plasma samples, optional serum banking sample and optional DNA banking sample if applicable (later sample may be collected at any time as of Visit 2). Refer to [Section 5.5](#)

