### [Section 5.5](#)

- Perform supervised PFTs
- Perform Study Drug Compliance Check
- Call IRT to dispense the open label medication kits (for further details refer to [Section 4.1.4](#))
- Instruct patient to take the first capsule of open label medication at the clinic under trial staff supervision. Refer to [Section 4.1.4](#) Instruct patient on further medication intake, please refer to [Section 4.2](#) regarding possible dose reductions, interruptions and management of drug related AEs.
- Schedule next planned clinic visit. Instruct patients to bring all study related treatments to the next clinic visit.

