6. GENERAL ANALYSIS DEFINITIONS

6.1 TREATMENT(S)

For treatment specifications, see Section 4 of CTP.

The following trial periods will be defined: screening, post-randomisation, blinded treatment period (with sub-periods off-treatment, post-treatment and follow-up), open-label treatment period (with sub-periods off-treatment, post-treatment and follow-up) and post-study as follows:

Note: Post-treatment reflects the residual effect period.

Note: the last day of each of the following periods is excluded.

- Screening: from informed consent to randomisation
- Post-randomisation (optional): from randomisation to first randomised trial drug intake in blinded treatment period
- Blinded treatment period: from first randomised trial drug intake (or re-start of treatment if interruption) to last randomised trial drug intake (or the day before start date of interruption, if interruption) plus one day
 - Blinded off-treatment (optional): from start date of interruption to re-start of blinded treatment
 - Blinded post-treatment (optional)^[a]: from the last blinded trial drug intake plus one day to last blinded trial drug intake plus 28 days plus one day or day of first open-label treatment administration (whichever occurs earlier)
 - Blinded follow-up (optional): from last blinded trial drug intake plus 29 days up to the beginning of post-study period. This period is only created if last blinded trial drug intake took place more than 28 days before trial completion, or for patients having prematurely discontinued the blinded treatment and still continuing the trial
- Open-label treatment period: from first open label nintedanib intake (or re-start of treatment if interruption) to last open label nintedanib intake (or the day before start date of interruption, if interruption) plus one day
 - Open-label off-treatment (optional): from start date of interruption to re-start of open-label treatment
 - Open-label post-treatment (optional)^[a]: from the last open-label trial drug intake plus one day to last open-label trial drug intake plus 28 days plus one day
 - Open-label follow-up (optional): from last open-label trial drug intake plus 29 days up to the beginning of post-study period. This period is only created if

last open-label trial drug intake took place more than 28 days before trial completion, or for patients having prematurely discontinued the open-label treatment and still continuing the trial

- Post-study: from the latest of

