For efficacy endpoints from baseline to week 12 (blinded period)	Baseline (see Section 6.7)	Visit 5 (after time windowing, refer to Section 6.7) Data up to the day after last blinded trial drug intake (included).

Table 6.1: 1 (continued) Summary of analysed periods according to the type of endpoint

	Studied period	
Analysed endpoint	Start date	End date^[1]
Rates of decline during blinded period	Baseline (see section 6.7)	Visit 5 (after time windowing, refer to Section 6.7) Data up to the day after last blinded trial drug intake (included).

Table 6.1: 1 (continued) Summary of analysed periods according to the type of endpoint

Analysed endpoint	Studied period	
	Start date	End date ^[1]
Rates of decline during open-label period	Visit 5 (start of open label treatment) Note: Covariates can be measured before Visit 5.	Visit 10 (after time windowing, refer to Section 6.7) Data up to the day after last trial open-label drug intake (included).

Table 6.1: 1 (continued) Summary of analysed periods according to the type of endpoint

	Studied period	
Analysed endpoint	Start date	End date^[1]
AEs and laboratory data		
On-treatment period safety (AEs, laboratory data, including enzymes elevation) during blinded treatment period	Date of first trial drug intake	First day of documented intake of open-label treatment or last blinded trial drug intake plus 28 days or end of treatment, whichever occurs first
	Off-treatment periods not excluded. However, for safety listings, anything happening during a treatment interruption will be flagged as occurring during the off-treatment period (even if between [last trial drug intake; last trial blinded drug intake + 28 days])	
On-treatment period safety (AEs, laboratory data, including enzymes elevation) during open label treatment period	First day of documented intake of open-label treatment	Last open label drug intake plus 28 days or end of treatment, whichever occurs first
	Off-treatment periods not excluded. However, for safety listings, anything happening during a treatment interruption will be flagged as occurring during the off-treatment period (even if between [last trial drug intake; last trial open label drug intake + 28 days])	
On-treatment period safety (AEs, laboratory data, including enzymes elevation) during overall treatment period	Date of first trial drug intake	Last drug intake plus 28 days or end of treatment, whichever occurs first

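### Pre-dose Visit 5 safety labs are counted as open-label nintedanib results, and the SAP disagrees with itself on whether they also stay in the blinded period

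*SAP*

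**What the plan says.** **Order of events at Visit 5.** Protocol 4.1.4 (Drug administration) states: "At all clinic visits the study drug will be administered at the study site (after any sampling procedures and PFTs". The general order of procedures in Protocol 6.2.2 agrees: blood first, medication last. The Visit 5 list includes "Perform safety laboratory collections and urine pregnancy test (if applicable" and later "Instruct patient to take the first capsule of open label medication at the clinic under trial staff supervision". Protocol 6.1 places all on-site visits in the morning, so the last blinded dose is normally taken the evening before.

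**Period list in SAP 6.1.** The list is headed by the rule "Note: the last day of each of the following periods is excluded". Its entries are:
- "Blinded treatment period: from first randomised trial drug intake (or re-start of treatment if interruption) to last randomised trial drug intake", plus one day.
- Blinded post-treatment, which runs until 28 days plus one further day after last blinded intake, "or day of first open-label treatment administration (whichever occurs earlier".
- "Open-label treatment period: from first open label nintedanib intake", with no time of day given.

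**Table 6.1:1, AE and laboratory rows.** The open-label row starts on "First day of documented intake of open-label treatment". The blinded row ends on that same day, or at last blinded intake plus 28 days, or at end of treatment, whichever is first. Neither row says whether the boundary day is included. The efficacy rows do say so: they include the day after last blinded intake.

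**Baseline.** SAP 6.7 uses the last assessment before first trial drug intake as baseline. The SAP text read here has no matching rule for the change-over to open-label drug.

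**The concern.** A sample taken before the first open-label capsule reflects 12 weeks of blinded treatment. For patients randomised to placebo it precedes any nintedanib in this trial. If the period label depends on the calendar day alone, that sample is reported under open-label nintedanib.

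The outputs at risk are those built on periods: on-treatment laboratory summaries, frequencies of abnormal values, individual maximum enzyme and bilirubin elevations, and time to first liver enzyme elevation (SAP 7.8.2). The Table 6.1:1 row for enzyme and bilirubin elevations that occur within 30 days of each other but in different periods is exposed too. Visits 4 and 5 are 28 days apart, so a raised transaminase at Visit 4 and a raised bilirubin at Visit 5, both on placebo, could be classed as spanning two periods.

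The first 12 weeks are the trial's only placebo-controlled safety data, and hepatic injury is an adverse event of special interest (Protocol 5.3.6.1). It should therefore be clear which period the week 12 draw belongs to.

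**Working it through.** The plan states no figure on this point, so there is nothing to reproduce. The check applies the SAP's rules to the scheduled days.

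**Inputs.**
- Visits 2, 3, 4 and 5 at weeks 0, 4, 8 and 12 (Protocol 6.1), i.e. days 1, 29, 57 and 85 with Visit 2 as day 1.
- Last blinded dose on the evening of day 84. First open-label dose on day 85, after the blood draw.
- Planned allocation 117 nintedanib and 233 placebo, 350 in total (Protocol 7.7).
- Scheduled post-baseline safety draws at Visits 3, 4 and 5 in the blinded phase and at Visits 6 to 10 afterwards (Protocol 6.2.2).

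**Reading A: the SAP 6.1 list, last day excluded.**
- Blinded treatment runs from day 1 up to but not including 84 + 1 = 85, so it covers days 1 to 84.
- Blinded post-treatment runs from day 85 up to but not including the earlier of 84 + 28 + 1 = 113 and 85. It is empty.
- Open-label starts on day 85.
- The Visit 5 draw is therefore open-label only.

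**Reading B: Table 6.1:1, end date inclusive.**
- The blinded row runs through the earlier of day 85 and 84 + 28 = 112, so day 85 is in.
- The open-label row starts on day 85, so day 85 is in there as well.
- The Visit 5 draw is in both periods.

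**Which reading does the wording favour?** Compare how each place writes the 28-day limit. The list says last intake plus 28 days plus one day, with that day excluded, so its last counted day is intake + 28. The table says last intake plus 28 days. With an inclusive end date its last counted day is intake + 28, which agrees with the list. With an exclusive end date it is intake + 27, which does not. This favours an inclusive table. Against that, only the efficacy rows say outright that a boundary day is included. The "End date" heading also carries a footnote whose text is not in the copy read here.

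**A variation.** If a patient took a blinded capsule on the morning of Visit 5, the list itself puts day 85 in both periods: blinded treatment then ends at 85 + 1, excluded, and open-label starts at 85.

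**Counts at planned N with full attendance.**

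| | Reading A | Reading B | Visit 5 in blinded period only |
|---|---|---|---|
| Blinded post-baseline draws per patient | 2 | 3 | 3 |
| Blinded draws, all patients | 2 × 350 = 700 | 3 × 350 = 1050 | 1050 |
| of which placebo | 2 × 233 = 466 | 3 × 233 = 699 | 699 |
| of which nintedanib | 2 × 117 = 234 | 3 × 117 = 351 | 351 |
| Open-label draws per patient | 6 | 6 | 5 |
| Placebo-exposed draws in the open-label period | 233 | 233 | 0 |

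Under both readings the Visit 5 draw is 1 of 6 scheduled open-label draws per patient. The two readings differ only in whether the blinded period keeps it.

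**The case against.** The strongest reply is that Table 6.1:1, to which SAP 6.1 refers for details, governs the laboratory analyses and follows its own convention. The exclusion note refers to the list of periods, and the 28-day comparison suggests inclusive end dates in the table. On that view the blinded analysis keeps all three draws. This stands. A reader might infer from the exclusion note that the placebo-controlled comparison loses a third of its laboratory data, or that about a third of first enzyme elevations change period. The documents do not establish the first. The second also needs elevations to be detected evenly across the three draws, which nothing in the documents supports.

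The reply does not reach the open-label side. Both the list and the table start that period on the Visit 5 day, so pre-dose samples enter it on either reading.

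Other limits also stand:
- The footnote text, the visit-window tables cited in SAP 6.7 and the definition of liver enzyme elevation (SAP 5.4.4) are not in the copy read here. One of them might settle the boundary.
- Safety analyses are descriptive, with no hypothesis testing. The overall treatment period contains Visit 5 on any reading.
- Vital signs are summarised by visit (SAP 7.8.3) and the Visit 5 list names no physical examination, so the point does not extend to them.
- Adverse events share the same boundary rows, but an event dated on the Visit 5 day may have begun before or after the capsule. The documents do not show that a link to a pre-dose finding is recorded, so a day-level rule for adverse events is not clearly better than the present one.

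**Conclusion.** The point holds for laboratory data. As written, the SAP counts pre-dose Visit 5 safety labs as open-label nintedanib results: up to 350 samples, of which up to 233 come from patients who had received only placebo in this trial. For patients randomised to nintedanib the exposure is nintedanib either way, and only the period label is wrong.

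The SAP is also inconsistent on the blinded side. The list drops the draw (2 of 3 kept), while the table appears to keep it and so counts it twice. The text available does not decide between these, so loss of a blinded draw is a possible consequence and not a demonstrated one.

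The counts are ceilings. They assume that every randomised patient attends Visit 5, has the blood draw and starts open-label drug that day. By-visit tables rest on re-calculated visits and overall-period summaries span both periods, so neither is affected. The primary and biomarker endpoints are also unaffected, because their rule includes the day after last blinded intake (day 85 here). This is a clarification worth making before unblinding. It is not a threat to the trial's main conclusions.

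**What to change.** In SAP 6.1 and in the blinded and open-label AE/laboratory rows of Table 6.1:1:

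1. State that laboratory samples dated on the day of first open-label intake, which are scheduled before the dose at Visit 5, belong to the blinded period only.
2. Start the open-label laboratory window after that sample.
3. Say in both places whether the boundary day is included, so that the list and the table agree.

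The cost is about one sentence, two table rows and one programming rule. No new data are needed. The small downside is that, with dates but no times, a rare unscheduled sample taken after the capsule on that day would be labelled blinded.

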#### **5.1.2 Secondary Endpoints**

The key secondary endpoint is the proportion of patients with disease progression as defined by absolute FVC (% predicted) decline  $\geq 10\%$  or death until week 52 based on in clinic supervised spirometry.

Secondary endpoints are the rate of change (slope) in blood C1M from baseline to week 12 and the rate of change (slope) in blood C3M from baseline to week 12.

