#### **Randomised Set (RS):**

The Randomised set (RS), consists of those patients who were randomised to a treatment group.

The efficacy and safety analysis will be conducted on the TS. Efficacy parameters will be analysed from an as randomised perspective and safety parameters from an as treated perspective, respectively. For efficacy analysis, all measurement performed within the first 12 weeks will be used. Efficacy evaluations done after lung transplant will not be used for the efficacy analyses; sensitivity analyses will be performed including these data.

Although there is no per protocol data set in the study, reasons for important protocol violations will be specified in the Trial Statistical Analysis Plan (TSAP). Patients with potential important protocol violations (those that relate to patient safety or efficacy) will be identified at Blinded Review Planning Meetings and listed in the clinical trial report.

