## **7.5 HANDLING OF MISSING DATA**

### **7.5.1 Efficacy endpoints**

In efficacy analyses of continuous endpoints, missing data will not be imputed. In the analyses of the time-to-event endpoints, missing or incomplete data are managed by standard survival analysis techniques. These will be described in detail in the TSAP.

In the analyses of the categorical endpoints, missing data will be imputed using the worst case.

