 - last trial drug intake plus 29 days
 - date of trial completion
 - follow-up visit
 - early end of treatment visit plus 1 day to database lock

^[a] In addition, a post-treatment period of 7 days will be used for adverse event analyses to more closely reflect the period of time after the last trial drug intake when measurable drug levels or pharmacodynamic effects are still likely to be present.

In addition to the above periods, the following additional period is defined:

- Overall: Combines all available data from Blinded treatment period and Open-label treatment period.

For safety analyses, data up to the end of the blinded / open-label post-treatment period will be considered on-treatment. For on-treatment efficacy analyses, data up to the day after last trial drug intake (included) will be considered.

For efficacy analyses patients will be assigned to the treatment group they were randomised to, for safety analyses patients will be assigned to the treatment group they were treated in.

Details are provided in [Table 6.1: 1](#).

Table 6.1: 1 Summary of analysed periods according to the type of endpoint

Analysed endpoint	Studied period	
	Start date	End date ^{1/1}
For primary analysis (rate of change (slope) in blood CRPM from baseline to week 12)	Baseline (see Section 6.7)	Visit 5 (after time windowing, refer to Section 6.7) Data up to the day after last blinded trial drug intake (included).
For the key secondary endpoint (Proportion of patients with disease progression as defined by absolute FVC (% predicted) decline $\geq 10\%$ or death until week 52)	Main analysis: Baseline (see Section 6.7) Sensitivity analysis: Visit 5 (start of open label treatment)	Visit 10 (after time windowing, refer to Section 6.7) Data up to the day after last open-label trial drug intake (included).
For secondary endpoints (rate of change (slope) in blood C1M and C3M from baseline to week 12)	Baseline (see Section 6.7)	Visit 5 (after time windowing, refer to Section 6.7) Data up to the day after last blinded trial drug intake (included).
For efficacy endpoints from week 12 to week 52 (open-label period)	Visit 5 (start of open label treatment) Note: Covariates can be measured before Visit 5.	Visit 10 (after time windowing, refer to Section 6.7) Data up to the day after last trial open-label drug intake (included).

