7.4 PRIMARY ENDPOINT

7.4.1 Primary analysis

Please refer to Section 7.3.1 of the CTP.

The primary analysis will be done on the TS.

All visits from baseline to week 12 will be included in the primary analysis, after time-windowing. Measurements after week 12 (after time windowing) are not taken into consideration for this endpoint.

Refer to [Section 9.1](#) for SAS code specifications.

Efficacy evaluations done after lung transplant will not be used for the efficacy analyses.

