7.5 SECONDARY ENDPOINT(S)

7.5.1 Key secondary endpoint(s)

The key secondary endpoint is defined as the proportion of patients with disease progression as defined by absolute FVC (% predicted) decline $\geq 10\%$ or death until week 52.

The following analyses are planned:

- Firstly, in order to assess the association of change in extracellular matrix (ECM) biomarker CRPM over 12 weeks with disease progression as defined by FVC decline $\geq 10\%$ or death over 52 weeks, a logistic regression analysis including baseline blood

CRPM and the rate of change (slope) in blood CRPM over the first 12 weeks as covariates will be applied **for the placebo treated patients only**.

By doing this, the potential of CRPM as a prognostic biomarker is evaluated.

- Secondly, in order to assess how Nintedanib treatment during the first 12 weeks affects the association between change in extracellular matrix (ECM) biomarker CRPM over 12 weeks and disease progression, a logistic regression analysis including baseline blood CRPM, rate of change (slope) in blood CRPM over the first 12 weeks, treatment and treatment CRPM slope interaction as covariates will be applied. **The interaction term will be of primary interest within this analysis.**
- Thirdly, in order to assess whether the overall treatment regimen affects disease progression as defined by FVC decline $\geq 10\%$ or death over 52 weeks, a logistic regression analysis including baseline blood CRPM and randomized treatment as covariates will be applied. **The treatment effect will be of primary interest within this analysis.**
- Fourthly, in order to assess whether rate of change (slope) in blood CRPM over the first 12 weeks to some extent explains the effect of treatment regimen on disease progression as defined by FVC decline $\geq 10\%$ or death over 52 weeks, a logistic regression analysis including baseline blood CRPM, rate of change (slope) in blood CRPM over the first 12 weeks and randomized treatment as covariates will be applied. **The treatment effect will be of primary interest within this analysis.**

Patients who died or progressed in the blinded phase are not at risk in the open label period, but will be considered in the main analysis (including their progression and/or death).

The four main analyses of the key secondary endpoint outlined at the beginning of this section will be repeated by replacing CRPM by C1M and C3M, respectively.

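### SAP Table 6.1:1 puts an on-treatment cut-off on the main analyses, which contradicts protocol 7.3 for the 12-week slopes and does not fit a key secondary endpoint that runs to week 52

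*SAP*

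**What the plan says.** SAP 6.1 defines the one-day rule in the text above Table 6.1:1: "For on-treatment efficacy analyses, data up to the day after last trial drug intake (included) will be considered". The table then uses it as the data limit for the main analyses. For the primary endpoint and the C1M and C3M slopes the limit is "Data up to the day after last blinded trial drug intake (included". For the key secondary endpoint, where one end date serves both the main and the sensitivity analysis, it is "Data up to the day after last open-label trial drug intake (included".

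Other sections set different limits:

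- Protocol 7.3: "For efficacy analysis, all measurement performed within the first 12 weeks will be used". The only exclusion stated there is for evaluations after lung transplant.
- SAP 7.4.1, for the primary: "All visits from baseline to week 12 will be included in the primary analysis, after time-windowing". SAP 7.5.2 handles C1M and C3M in the same way.
- Protocol 5.1.2 and SAP 5.2.1 define the key secondary endpoint as an FVC decline "or death until week 52 based on in clinic supervised spirometry".
- SAP 7.5.1 says patients who progress or die in the blinded phase "will be considered in the main analysis (including their progression and/or death".
- Protocol 7.5.1: "In the analyses of the categorical endpoints, missing data will be imputed using the worst case". SAP 6.6 says the same for binary endpoints.
- SAP Section 4, which is reserved for departures from the protocol, declares none.

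The protocol also plans to collect data after discontinuation. Sections 3.1, 3.3.4.1 and 6.2.3 ask patients who stop drug to keep attending visits, and 6.2.3 seeks vital status at week 52 from those who decline.

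**The concern.** A programmer following Table 6.1:1 and one following protocol 7.3 would build different data sets for the same confirmatory test. Patients stop drug for adverse events and other medical reasons (protocol 3.3.4.1), so data removed at stopping are unlikely to be a random subset.

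The key secondary endpoint is the more exposed, and it is the one that sets n = 350. Three things are unresolved:

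- Deaths and FVC declines after the last open-label dose fall outside the window. For example, protocol 4.2.1.4 lets drug be interrupted during an acute exacerbation. If the patient dies two or more days after the last dose without resuming, the death is not counted.
- The end date is undefined for a patient who never takes open-label drug, although SAP 7.5.1 counts that patient's blinded-phase events.
- Nothing visible says whether observed data beyond the cut-off count as missing. If they do, worst-case imputation replaces an observed progression-free outcome at week 52 with progression.

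**Working it through.** **Who is affected.** Completers are not cut off: they take the first open-label dose at Visit 5 and the last dose at Visit 10 (protocol 6.2.2). Interruptions that are later resumed are not cut off either. For the 12-week slopes, the rule affects only patients who stop blinded drug and do not resume before a scheduled sample. For the key secondary endpoint, it affects patients who stop before week 52 and those who never start open-label drug.

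**Step 1: reproduce the plan's power.** Inputs from protocol 7.7: 233 placebo patients in two about equal slope groups (116.5 each), 30% versus 50% progression, two-sided 5%.

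Power = Φ[(Δ − 1.96·SE0)/SE1], with SE0 = √(2·p̄(1−p̄)/n) and SE1 = √([p1(1−p1)+p2(1−p2)]/n).

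SE0 = √(2×0.4×0.6/116.5) = 0.0642; SE1 = √((0.21+0.25)/116.5) = 0.0628; (0.2 − 0.1258)/0.0628 = 1.18. Power is 88.1%, against 88% stated.

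**Step 2: worst-case scoring.** The documents give no stopping rate, so a range is assumed, equal in both slope groups. If a share s is scored as progressed, each group's rate becomes p(1−s)+s.

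| s | Rates | Power |
|---|---|---|
| 0 | 30.0% vs 50.0% | 88.1% |
| 5% | 33.5% vs 52.5% | 83.8% |
| 10% | 37.0% vs 55.0% | 79.1% |
| 20% | 44.0% vs 60.0% | 68.8% |

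**Step 3: what using observed data recovers.** Let S be the share stopping and f the share of stoppers followed to week 52. The cut-off gives s = S. Using observed data gives s = S(1−f).

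| S | Cut-off | f = 1 | f = 0.5 | f = 0 |
|---|---|---|---|---|
| 10% | 79.1% | 88.1% | 83.8% | 79.1% |
| 20% | 68.8% | 88.1% | 79.1% | 68.8% |

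With half followed, the gain is 83.8 − 79.1 = 4.7 points, or 79.1 − 68.8 = 10.3 points. At the protocol's 40% overall progression rate, the number seen progression-free but scored as progressed is 233×S×f×0.6: 233×0.10×0.5×0.6 = 7.0, or 233×0.20×0.5×0.6 = 14.0.

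**Step 4: other readings of the cut-off.** Here the affected patients are assumed to have had no earlier event. If they count as non-events, power is 82.1% (10%) or 74.8% (20%). If they are dropped, it is 84.6% or 80.1%.

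**Step 5: the planned model.** SAP 7.5.1 uses logistic regression on continuous slope. This was simulated with a standardised slope X ~ N(0,1) and logit p = −0.435 + 0.547X, which gives 30% and 50% on a median split. Other settings were n = 233, a Wald test and 8,000 runs, with baseline CRPM omitted and a share s set to progressed at random. Power is 97.9, 95.5, 93.2 and 85.7% for s = 0, 5, 10 and 20%. The largest Monte Carlo standard error is √(0.857×0.143/8000) = 0.4 points.

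**Step 6: the primary.** With samples at weeks 0, 4, 8 and 12, the sum of squares of time is 36+4+4+36 = 80. Without week 12 it is 16+0+16 = 32. Let r be the between-patient slope variance relative to the sampling variance of a full four-sample slope. The information lost per affected patient is 1 − (r/80+1/80)/(r/80+1/32), which is 60.0, 42.9 and 23.1% for r = 0, 1 and 4. If 10% of patients lose a collected week-12 sample, 94.0 to 97.7% of the information is kept. For a 20% difference and SD 50% with 117 and 233 patients, power moves from 94.2% to between 92.8 and 93.7%.

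**The case against.** - **Scope.** Protocol 7.3 speaks of the first 12 weeks and SAP 7.4.1 of the primary only, so neither governs the week-52 endpoint. This stands. For the key secondary endpoint, the conflict is with its own definition, the planned follow-up and SAP 7.5.1.
- **Reading of 7.4.1.** It may only fix the visit range, with Table 6.1:1 supplying the data limit. That is possible, but 7.4.1 does not say so, and protocol 7.3 would still conflict.
- **Unseen text.** Footnote [1] on the end-date column is not shown and could qualify these rows. Other parts of the SAP are also not shown, so an all-data or on-treatment sensitivity analysis may already exist. This is a real limit on certainty. A sensitivity analysis elsewhere would not change the main-analysis rows.
- **The harms are alternatives.** Under worst case, a patient who dies or progresses after stopping is scored correctly, and only progression-free patients are misclassified. If later data are simply ignored, worst case overwrites nothing, but observed events are lost. This stands; Step 4 gives the figures for the other readings.
- **Size.** The two-group comparison is a sample-size device. In the planned model, with 10% stopping and half followed, the gain is about 2 points (95.5% against 93.2%). The counts of 7 and 14 assume that stoppers progress at the average rate, which selective stopping could alter.
- **Remedy.** Off-drug values dilute the comparison, and nintedanib or pirfenidone is permitted after early end of treatment (protocol Table 4.2.2.1:1). Placebo-arm CRPM taken on non-trial nintedanib would work against the reason for a placebo-only analysis. This is a fair cost, and a reason to keep the on-treatment version as a sensitivity analysis.

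**Conclusion.** The concern holds and should be fixed. For the CRPM, C1M and C3M slopes, Table 6.1:1 contradicts protocol 7.3, and for the primary also SAP 7.4.1 as worded, with no change declared. For the key secondary endpoint, the cut-off does not fit follow-up to week 52, has no end date for patients never on open-label drug, and interacts with worst-case imputation in an unstated way.

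The textual conflict needs no assumption beyond footnote [1] not altering the rows. No figure stated in the plan is wrong. The size is illustrative because it rests on assumed stopping and follow-up rates. The effect on the primary is small, and power there stays above 90%. The effect on the key secondary endpoint ranges from modest in the planned model to material in the protocol's sizing comparison, and only patients followed after stopping are recoverable. Confidence is medium, mainly because of the unseen footnote.

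**What to change.** Align Table 6.1:1 with protocol 7.3 and the endpoint definition:

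- For the slopes, use all CRPM, C1M and C3M samples to Visit 5 taken before the first open-label dose, regardless of discontinuation.
- For the key secondary endpoint, use all clinic FVC values and all deaths to week 52, regardless of discontinuation.
- Leave the post-transplant exclusion as it is.
- State that worst case applies only where the week-52 outcome was not observed.
- Keep the day-after-last-dose limit as a labelled on-treatment sensitivity analysis, with a defined end date for patients who never took open-label drug.

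If the sponsor prefers the cut-off as the main analysis, declare and justify it in SAP Section 4, align 7.4.1, and say whether observed data beyond it count as missing.

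The cost is SAP wording and one sensitivity run, since the protocol already plans to collect the data. The downside is the dilution from off-drug values and post-stopping therapy, which the sensitivity analysis would show.
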